There may be unforeseeable risks to the embryo or fetus, for both male and female subjects in this study. Subsequently, extreme care must be taken to avoid pregnancy in female subjects during this study for up to 30 days following completion of study treatment as well as in female partners of male subjects during this study for up to 90 days following completion of study treatment.

In addition to the risks listed above, there are risks that are not known or do not happen often when subjects take TAF, including severe or life-threatening allergic reactions, or interactions with another medication. Subjects will be informed in a timely manner, both verbally and in writing of any new information or changes to the way the research will be done that might influence their willingness to continue to take part in this study.

For more details on adverse reactions please see the Vemlidy® package insert for more information.

Benefits: The medical knowledge gained may be able to guide future research, clinical trial planning, and guideline recommendation for this patient population.

3. Study Overview

Dosage regimen: Patients on any antiviral treatment for chronic HBV who plan to be switched by their physician to be treated with TAF 25 mg for 24 months will be enrolled. Any treatment after will be up to the physician's discretion. The drug will be administered orally, per manufacturers' instructions, and can be taken with food.

Compliance: Patients will be enrolled and monitored according to the protocol, GCP, and clinical practice guidelines.

Study population: Approximately 251 adult patients currently on antiviral therapy and are planned to be switched to TAF by their physicians will receive TAF 25 mg. Enrollment goal will be approximately 185 for prior entecavir patients, 33 for prior tenofovir (TDF) patients and 33 for prior combination therapy patients (any oral nucleos(t)ide combination). Enrollment goal for entecavir is based on relative lack of data for sequential entecavir to TAF therapy. Enrollment goal for TDF is used to avoid bias and as a comparison. Enrollment goal for combination therapy is based on estimates of the small patient population with CHB maintained on long term combination therapy.

Inclusion criteria:

1. Male or female, age ≥ 18 years
2. CHB diagnosis confirmed by positive HBsAg or HBV DNA or HBeAg or documented history of CHB in physician note

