3. Currently maintained on antiviral therapy for at least 48 weeks with any HBV DNA value at Screening/Baseline and planned to be switched to TAF by their physician

4. Routinely monitored for serum HBV DNA PCR, liver chemistry, renal chemistry including by their physicians every 3-6 months and a bone density scan at least every 2 years as per routine clinical care (one at baseline and one 2 years after switch).
5. Estimated creatinine clearance $> 15 \text{ ml/min}$ for men or $> 12.75 \text{ ml/min}$ for women (using the Cockcroft-Gault method) at Screening/Baseline Visit
6. Willing and able to provide informed consent
7. Able to comply with dosing instructions for study drug administration and able to complete the study schedule of assessments

Exclusion criteria:

1. Pregnant women, women who are breastfeeding or who believe they may wish to become pregnant during the course of the study
2. Previous recipient of a liver transplant
3. Co-infection with human immunodeficiency virus (HIV) or hepatitis C (HCV) or hepatitis D (HDV)
4. Severe or uncontrolled comorbidities
5. Current or known hepatic decompensation (≤ 2 years) (e.g ascites, encephalopathy, or variceal hemorrhage) with a Child-Pugh score of B or C
6. Malignancy including liver cancer within 5 years except cancers easily curable by surgical resection (e.g. basal cell skin cancer and squamous cell cancer)
7. Currently receiving any immunosuppressive therapy
8. On any of the disallowed concomitant medications listed in the prior and concomitant medications list (pg. 13). Subjects on prohibited medications who are otherwise eligible will need a wash out period of at least 30 days prior to the Screening/Baseline visit.
9. Males and females of reproductive potential who are unwilling to use “effective” protocol-specified method(s) of contraception during the study.
10. Current substance or alcohol abuse judged by the investigator to potentially interfere with subject compliance.
11. Any other clinical conditions that, in the opinion of the Investigator, would make the subject unsuitable or unable to comply with any of the study procedures

4. Study Objectives

Primary objective:

- To describe rate of persistence and/or improvement of viral suppression with TAF as with previous anti-HBV treatment

Secondary objective:

- To describe persistence of ALT normalization and/or improvement of ALT levels with TAF as with previous anti-HBV treatment

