- To describe trends in serum creatinine and calculated creatinine clearance as available by local labs.
- To describe trends in bone mass from baseline to 24 months after switch.

5. Study Design

Study design: Open label prospective interventional cohort study.

Study Timelines:

[figure not shown]
- Total study duration: 36 months
- Study Start-Up: 3 months
- Patient enrollment: 6 months
- Patient follow-up: 24 months
- Final analysis & Manuscript Preparation: 3 months
- Publication plan: Interim analysis 2018 – 2019, Final analysis 2020

Primary endpoint: Rate of viral suppression at 6, 12, 18, 24 months after switch, as available.

Secondary endpoints(s):

- ALT levels at 6, 12, 18, 24 months after switch
- Serum creatinine, calculated creatinine clearance (Cockcroft-Gault) at 6, 12, 18, 24 months after switch
- % change in bone mineral density from baseline to 24 months after switch

Study schematic:

Study protocol: Treatment Outcomes in Chronic Hepatitis B Patients on Sequential Therapy with Tenofovir Alafenamide

The following table below describes all study procedures:

Study protocol: Treatment Outcomes in Chronic Hepatitis B Patients on Sequential Therapy with Tenofovir Alafenamide

Study Procedures	Screening/Baseline	Treatment Months*							
		3*	6	9*	12	15*	18	21*	24/ED
Informed Consent	X								
Inclusion/ Exclusion Criteria	X								
Medical History ¹	X								
Vital Signs	X		X		X		X		X
Physical Examination	X		X		X		X		X
Adverse Events			X		X		X		X
Concomitant Medications	X		X		X		X		X
Bone Density Scan (DEXA) ^{4,5}	X								X
HBeAg ²	X		X		X		X		X
HBV DNA PCR	X	X	X	X	X	X	X	X	X
α -fetoprotein (AFP)	X		X		X		X		X
Ultrasound (to rule out HCC)	X		X		X		X		X
International Normalized Ratio (INR) ³	X				X				X
CBC Panel with WBC, Hb, Platelet, HCT	X		X		X		X		X
Complete Metabolic Panel with Na, K, Cr, Tb, CO2/HCO3, BUN, GLU, AST, ALT, ALK, ALBU	X	X	X	X	X	X	X	X	X
Serum Phosphorus	X	X	X	X	X	X	X	X	X
Fasting Cholesterol Panel with Total Cholesterol, HDL, direct LDL, TG	X		X		X		X		X
Vitamin D Assessment	X								
Fibrotest, Fibrosure, Fibrospect, FIB-4 or Elastography	X								
HCV, HDV, HIV Testing ⁶	X								
Urinalysis	X	X	X	X	X	X	X	X	X

Study protocol: Treatment Outcomes in Chronic Hepatitis B Patients on Sequential Therapy with Tenofovir Alafenamide

Data capture/case report forms	X		X		X		X		X
Study Drug Dispensing	X		X		X		X		X

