*Every visit can be 3-6 months as per routine clinical care. Clinical visit for Month 3 is optional but Month 3 lab is required for all sites. Month 9, 15, and 21 labs are optional.

1. For women of childbearing potential, last menstrual period must be documented
2. HBeAg serology to be done only in patients with positive HBeAg at Screening
3. INR testing to be done only in cirrhotic patients
4. Bone density scan will be charged and billed to the study as applicable.
5. Additional scan at 12 months is optional per investigator.
6. HCV RNA or antibody testing can be used to rule out co-infection. HDV and HIV antibody test are optional if test is not available to order at site or is not routinely performed.

Study Procedures:

Pre-Screening: Patients who are planned to be switched from their current antiviral therapy to TAF will be identified by their primary physician and approached to enroll in this prospective interventional cohort study. If a patient is deemed eligible to participate, the site will evaluate the potential patient using the inclusion/exclusion criteria and fill out the CRF for the screening visit. The local coordinator will transmit the pre-screening data to the central coordinator prior to the actual screening/baseline visit. If the patient is deemed eligible by the sponsor, the patient will be given a study ID and allowed to enter the study.

Screening/Baseline: Written and informed consent will be obtained prior to any study protocol related procedures or data abstraction. If patient has been pre-screened approved and all lab data are available they will begin treatment with TAF on the screening/baseline visit. The screening/baseline visit consists of obtaining written and informed consent, reviewing the inclusion/exclusion criteria, confirming medical history, completing a physical examination with vital signs and body weight, reviewing any concomitant medications and study drug dispensing. HBV DNA can be done within 3 months prior to study enrollment and Vitamin D assessment can be done within 12 prior to study enrollment. Serum AFP and liver ultrasound can be done within 6 months prior to enrollment. DEXA scan can also be done within 6 months prior to enrollment.

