Procedures: In general, labs should include CBC (complete blood count, e.g. WBC, PLT, Hb, HCT), CMP (complete metabolic panel, e.g. CO₂ or HCO₃⁻, Na⁺, K⁺, Creatinine, Albumin, ALT, AST, ALK, Glucose, Total Bilirubin, BUN, Serum Phosphorous), INR (international normalized ratio), AFP (alpha-fetoprotein), fasting cholesterol panel, (e.g. Total cholesterol, HDL, direct LDL, Triglycerides (TG), Urinalysis, HBV DNA quantification and HBeAg status. Screening will also include HCV, HIV and HDV testing, if not previously done. All laboratory tests including the DEXA scan for all sites except South Korea will be ordered and billed as per routine care. For South Korea, all laboratory and DEXA scans will be ordered and billed to the study per standard of procedures in South Korea for all studies that provide medication. For Taiwan and the US, all DEXA scans will be ordered and billed to the study. Blood will be drawn at the site at which the patient was recruited, and processed by a lab technician in the clinical laboratory at that respective site. Standard of care for HCC surveillance should include radiology and AFP every 6 months per AASLD and APASL guidelines. All scans should be billed to patient's insurance or patient. At site PI's discretion, higher level imaging or frequency can be done.

Treatment Visits: Treatment will consist of taking TAF 25 mg daily with food for 24 months. Treatment visits will occur at approximately every 3-6 months as per routine clinical care, except for those listed in section 13. Clinical visit for Month 3 is optional but Month 3 lab is required for all sites. Month 9, 15, and 21 labs are optional. Each visit will consist of reviewing adverse

events and concomitant medications, completing a physical examination with vital signs and body weight, completing all necessary routine labs including DEXA scan and study drug dispensing. At every visit the patient must bring all study drugs (including empty bottles) so that the study staff can count compliance using the number of remaining pills.

This schedule of clinic visits and laboratory tests are routine and standard practice for investigators in their treatment of similar patients with CHB. Patients will be encouraged to adhere to these recommendations. Results of these laboratory tests and clinical evaluations will be recorded as well as any additional evaluations that are done as part of the patient's clinical care that are pertinent to the objective of the study.

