If a specific medical diagnosis has been made, that diagnosis or syndrome should be recorded as the adverse event, whenever possible. However, a complete description of the signs, symptoms and investigations which led to the diagnosis should be provided. For example, if clinically significant elevations of liver function tests are known to be secondary to hepatitis, "hepatitis" and not "elevated liver function tests" should be recorded. If the cause is not known, the abnormal test or finding should be recorded as an adverse event, using appropriate medical terminology (e/g/ thrombocytopenia, peripheral edema).

Maintenance of Safety Information: Safety information will be maintained in a clinical database/repository in a retrievable format. At a minimum, at the end of the treatment phase ("last patient off treatment") as well as the end of the follow-up phase ("last patient out") of

the study, [name] shall provide all adverse events, both serious and non-serious, in report format.

Reporting Timelines: All safety information covered in SAEs should be reported within **24 hours** of becoming aware of the event(s) to the sponsor. All non-serious AEs should be recorded in a CRF and reported to the site's IRB as per their guidelines for prompt reporting.

Pregnancy Precaution and Contraceptive Requirements: Because the full effects of TAF on an unborn baby or a nursing infant are not known, any female who is pregnant or breast feeding an infant will not be enrolled in this study. Female subjects must also refrain from egg donation and in vitro fertilization during treatment and until at least 30 days after the end of relevant systemic exposure.

If a subject becomes pregnant or suspects that they have become pregnant while in the study or within 30 days after the last dose of study drug, they must stop taking all the study drugs and notify their study doctor immediately. They will be discontinued from the study. If their partner becomes pregnant while they are in the study, the subject must notify the study doctor immediately. The study doctor will request to track the pregnancy and will report the pregnancy to the Study Sponsor.

If a subject is a sexually active female, it is required that they use an effective method of birth control from the Screening/Baseline visit as well as during the study and for at least 30 days after stopping the last dose of study drug. Effective protocol specified methods of birth control in this study are as follows:

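### Pregnancy is an exclusion, but the plan schedules no pregnancy test to verify it, so a woman with an early or unrecognised pregnancy can be enrolled and given TAF

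*Combined protocol and SAP*

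**What the plan says.** Section 3, exclusion criterion 1, bars "Pregnant women, women who are breastfeeding or who believe they may wish to become pregnant during the course of the study". Section 7, under pregnancy precautions, restates the bar as an outcome: "any female who is pregnant or breast feeding an infant will not be enrolled in this study". The summary of risks that precedes Section 3 gives the reason. It describes possible unforeseeable risk to an embryo or fetus and says that "extreme care must be taken to avoid pregnancy in female subjects during this study".

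The schedule table in Section 5 is introduced as covering all study procedures, and it has no pregnancy-test row. Footnote 1 reads "For women of childbearing potential, last menstrual period must be documented". It is attached to the row "Medical History ¹", which is marked at Screening/Baseline only.

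The Section 5 text for that visit lists consent and review of the criteria, then "confirming medical history, completing a physical examination with vital signs and body weight, reviewing any concomitant medications and study drug dispensing". A subject who has been approved at pre-screening and whose laboratory data are available starts TAF at that visit. The laboratory list ends with "Urinalysis, HBV DNA quantification and HBeAg status" and continues: "Screening will also include HCV, HIV and HDV testing, if not previously done". Neither sentence mentions pregnancy.

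Two safeguards apply after entry. Exclusion 9 and Section 7 require effective contraception, for sexually active women from the Screening/Baseline visit onward. Section 7 also requires a subject who is or suspects she is pregnant to stop study drug and tell the study doctor. She is then discontinued.

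**The concern.** An eligibility criterion is only as good as the procedure used to apply it. Here the protocol asserts that no pregnant woman will enter and gives a serious reason, but the procedure it supplies is a recorded date. The plan does not say what date should raise doubt or what the site should do about it. Early pregnancy is the case that a history is most likely to miss, and drug can be started at the visit where the history is taken.

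What is at stake is mainly safety: fetal exposure to TAF under a protocol that says it will not enrol pregnant women. There is also a smaller consequence for the data. A pregnancy present at entry and found later leads to discontinuation under Section 7, and Section 8 limits the analyses to eligible subjects who have not been withdrawn.

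**Working it through.** The plan states no figure on this point, so there is none to reproduce. The check is a search for any pregnancy test, followed by a comparison of the relevant places.

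**1. Search.**

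| Place | What bears on pregnancy status | Pregnancy test? |
|---|---|---|
| Section 3, exclusions 1 and 9 | Pregnancy excluded; contraception required | No |
| Section 5, schedule table (Screening/Baseline, Months 3, 6, 9, 12, 15, 18, 21, 24/ED) | Footnote 1 on Medical History, Screening/Baseline only | No, 0 of 9 time points |
| Section 5, screening visit, laboratory list and treatment visits | History, physical examination; urinalysis with no pregnancy component stated | No |
| Section 6, Early Discontinuation visit and follow-up | Examination, medications, adverse events, routine tests | No |
| Section 7, pregnancy precautions | Contraception, self-report, discontinuation | No |

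The count is zero pregnancy tests over nine time points, and one menstrual-date record, at entry. The opening part of the document was not available. The complete eligibility, schedule, procedures and pregnancy sections were.

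**2. What each safeguard can detect at entry.**

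- *Menstrual date.* A clearly late period may prompt a question. A recent, misremembered or irregular date will not, and no action is attached to either answer.
- *Contraception.* The requirement runs from Screening/Baseline. It reduces later conception and does not reveal a pregnancy that already exists.
- *Self-report.* This depends on the subject knowing or suspecting, so it fails by definition for an unrecognised pregnancy.

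None of the three reliably identifies an early pregnancy before the first dose.

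**3. Comparison with other criteria.** Creatinine clearance (inclusion 5) is supported by the metabolic panel. Co-infection (exclusion 3) has its own schedule row and a footnote on acceptable tests, although HDV and HIV tests become optional where a site cannot order them or does not do them routinely. Pregnancy can also be tested objectively, but it has no row.

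**4. Size.** The documents give neither the number of women of childbearing potential nor a pregnancy rate, so the expected number of unrecognised pregnancies at entry cannot be computed. The number of women who would be tested can only be illustrated. If 10% to 20% of the 251 planned subjects were women of childbearing potential (an assumption with no basis in the documents), that is 0.10 × 251 = 25.1 to 0.20 × 251 = 50.2, or about 25 to 50 women. This range sizes the cost of the fix, not the harm.

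**The case against.** The strongest reply is that the study overlays routine care. Every subject has had at least 48 weeks of antiviral therapy, and her physician already planned the switch to TAF, so exposure is not wholly created by the study. Sites review the criteria, take a history, examine the patient and obtain sponsor approval at pre-screening. Section 3 requires enrolment and monitoring according to GCP and practice guidelines. A physician who sees a late period may well order a test.

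Much of this stands, and it rules out several stronger readings that a reader might infer:

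- *That the whole 24 months of treatment rest on the menstrual date.* They do not. The date is a baseline item, and after that the plan relies on required contraception and self-report.
- *That an unrecognised pregnancy will be enrolled, or that sites have no means of applying exclusion 1.* The documents support only that it can happen. History, examination or local testing may catch some cases.
- *That 25 to 50 women would be harmed, or would start drug on a recalled date alone.* That range counts assumed women of childbearing potential, who must also accept contraception. It does not count pregnancies, and the true number of unrecognised pregnancies could be zero.
- *That the 24-month endpoints are materially damaged.* Section 6 collects viral, renal and bone data on withdrawn subjects who are not lost to follow-up. Leaving withdrawn subjects out of the analyses is a separate matter, and no material effect on the endpoints is shown here.

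The reply does not supply a required means of verification. Testing under routine care is possible but nowhere mandated. The protocol calls itself interventional, provides the drug outside Japan, and chose to set the exclusion and assert its result.

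**Conclusion.** The point holds as a gap between a stated exclusion and the procedure meant to apply it. The only scheduled check is one menstrual date at entry with no consequence attached, and TAF can start at the same visit. A site in full compliance can therefore enrol and dose a woman with an early or unrecognised pregnancy.

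This goes beyond missing detail, because the plan does name a method and that method cannot reliably deliver the exclusion. The number affected cannot be derived. The case for change rests on the seriousness the protocol itself attaches to fetal exposure and on how little a baseline check would cost. The conclusion assumes that the unavailable opening pages do not add a pregnancy test to the schedule.

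**What to change.** Add a row to the Section 5 schedule, marked in the Screening/Baseline column, for a urine pregnancy test in women of childbearing potential, used to verify exclusion 1. Amend footnote 1 and exclusion 1 to refer to its result. Tie the test to the visit and not to study-drug dispensing, because the Japan sites prescribe TAF through insurance and receive no study drug.

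The protocol must also reconcile the call for extreme care in the risk summary, exclusion 1 and the Section 7 statement with the Section 5 schedule on how pregnancy status is established during treatment. The sponsor should set that rule.

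The cost is one schedule row, two wording changes and a small charge per test, for about 25 to 50 tests under the illustrative 10% to 20% assumption. No extra visit or staff is needed. Urinalysis is already scheduled at Screening/Baseline, but laboratory data may predate the visit, so a fresh sample will sometimes be needed. Because Sections 5 and 13 bill laboratory work differently by country, the amendment should say whether the study or routine care pays in each.

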For each subject, AEs and SAEs should be recorded after informed consent is obtained until the subject has completed participation in the study as follows:

- A serious adverse event must be reported if it occurs during a subject's participation in the study and within **30 days** of receiving the last dose of study drug.
- Any serious adverse event that is ongoing when a subject completes his/her participation in the study must be followed until any of the following occurs:
 - The event resolves or stabilizes;
 - The event returns to baseline condition or value (if a baseline value is available);
 - The event can be attributed to agents(s) other than the study drug, or to factors unrelated to study conduct.

Recording of Adverse Events, Serious Adverse Events: Recording should be done in a concise manner using standard, acceptable medical terms. The adverse event recorded should not be a procedure or a clinical measurement (i.e. a laboratory value or vital sign) but should reflect the reason for the procedure or the diagnosis based on the abnormal measurement. Preexisting conditions that worsen in severity or frequency during the study should also be recorded (a preexisting condition that does not worsen is not an adverse event).

Furthermore, a procedure or surgery is not an adverse event; rather, the event leading to the procedure or surgery is considered an adverse event. Any event requiring in-patient hospitalization that occurs during the course of a subject's participation in a trial must be reported as an SAE. Hospitalizations that do not meet the criteria for SAE reporting are:

- Reasons described in the Protocol, e.g. drug administration, Protocol-required testing
- Surgery or procedure planned prior to entry into the study.

If, in [name] judgment, a clinical significant worsening from baseline is observed in any laboratory or other test parameter, physical exam finding, or vital sign, a corresponding clinical adverse event should be recorded.

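### Exclusion 8 puts a study-driven washout of at least 30 days before the only scheduled consent, and so before AE/SAE recording

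*Combined protocol and SAP*

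**What the plan says.** **Washout.** Exclusion criterion 8 in Section 3 bars patients on the disallowed concomitant medications, but lets those who otherwise qualify enter after a washout. They "will need a wash out period of at least 30 days prior to the Screening/Baseline visit".

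**Consent.** In the Section 5 procedures table, informed consent has one mark, in the Screening/Baseline column. The text agrees: "The screening/baseline visit consists of obtaining written and informed consent". TAF may start at the same visit. The same paragraph also gives a general rule: "Written and informed consent will be obtained prior to any study protocol related procedures or data abstraction". Section 6 adds that consent comes before study initiation.

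**Before that visit.** Under Pre-Screening in Section 5, patients are approached about enrolling, and "the site will evaluate the potential patient using the inclusion/exclusion criteria and fill out the CRF for the screening visit". Then "The local coordinator will transmit the pre-screening data to the central coordinator prior to the actual screening/baseline visit". Consent is not mentioned at this step.

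**Safety recording.** Section 7 states that "AEs and SAEs should be recorded after informed consent is obtained until the subject has completed participation in the study".

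**Physician's role.** Prior and Concomitant Medications in Section 5 leaves non-permitted drugs to the treating physician's judgment, and then lists disallowed drugs, among them phenytoin and rifampin.

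**The concern.** The washout is a condition of entry, and it has to be finished by the visit at which consent is first scheduled. A patient who stops a medicine only to meet exclusion 8 would therefore be acting on a study requirement before agreeing to take part. Because recording starts at consent, anything that happens during the withdrawal would also go unrecorded by the study.

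For some of the listed drugs, stopping is not trivial. Phenytoin and rifampin are on the list, and no other exclusion criterion names them, so a patient taking either could reach this route unless an investigator judges the patient unsuitable on other grounds. What is at stake is consent and patient safety during the withdrawal. The viral suppression, ALT, renal and bone endpoints are not in question.

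**Working it through.** There is no planned figure to reproduce. The check is a timeline, with the Screening/Baseline visit as Day 0.

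| Step | Source | Day |
|---|---|---|
| Latest start of washout | Exclusion 8, Section 3 | 0 − 30 = −30 (or earlier) |
| Washout complete | Exclusion 8, Section 3 | 0 |
| Only scheduled consent | Procedures table and Screening/Baseline text, Section 5 | 0 |
| AE/SAE recording begins | Section 7 | at consent, so 0 |
| Earliest TAF start | Screening/Baseline text, Section 5 | 0 |

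1. Time in washout before scheduled consent: 0 − (−30) = 30 days at minimum.
2. Time in washout outside AE/SAE recording: recording begins at consent, so this is the same 30 days at minimum.
3. Total exposure: with n patients who wash out solely for eligibility, at least 30 × n patient-days. The documents do not give n. It may be zero, and the total is then zero.

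The next question is whether the provisions can all be met together. Take three of them: (a) washout ends at or before Day 0; (b) consent is taken on Day 0; (c) consent precedes every protocol-related procedure. A washout undertaken only to satisfy an eligibility criterion is protocol-related. Under (a) and (b) it precedes consent, and under (c) it must follow consent. All three cannot hold for such a patient, so a site must set one aside.

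Does (c) settle the matter by moving consent earlier? Not clearly. It stands in the paragraph that describes the Screening/Baseline visit, does not mention washout, and provides no earlier consent step. The Pre-Screening paragraph just above it has sites apply the criteria, complete a CRF and send data ahead of the visit without mentioning consent. A site could read that as meaning that steps before the visit need no consent. Two sites acting in good faith could time consent differently.

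**The case against.** The strongest reply is that the protocol already forbids the harm. An eligibility-only washout is a protocol-related procedure, so the general rule requires consent first. Section 3 commits the study to GCP, nothing prevents earlier signing, and the pre-screening approach offers a natural occasion for it. On this view a site reaches an unconsented washout only by breaking a stated rule. Much of this stands: the protocol contradicts itself and does not openly allow withdrawal without consent. But a rule that the schedule contradicts is weak protection, and stating its application to washout costs little.

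A second reply is that few patients are affected. Every participant is already due to switch to TAF on a physician's advice. Some listed drugs are expected to reduce TAF's effect, so stopping them may simply be part of the clinical switch. Immunosuppressants are excluded separately. This stands as a limit on size. It does not remove the case in which a drug is stopped only to qualify.

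Two stronger readings are tempting, and the documents support neither.

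- The "Adverse Events" row of the procedures table is blank at Screening/Baseline and first marked at Month 6, so a reader might infer that the unrecorded period runs until then. It does not. Section 7 has recording in force from consent onward, so time after Screening/Baseline is covered whatever the table marks.
- A reader might also infer that, even with earlier consent, no visit would pick up washout events. Section 7, under assessment of safety, calls for safety to be assessed whenever a patient attends clinic, and Screening/Baseline is such an attendance.

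**Conclusion.** The point holds. Followed as scheduled, a washout done solely for study eligibility runs for at least 30 days before consent and before AE/SAE recording, contrary to the protocol's own consent rule.

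The conclusion rests on three conditions. The stop must be made for eligibility and not as ordinary care. The site must follow the scheduled consent visit and not sign earlier on its own initiative. And nothing in the consent form, which was not available for this review, may already deal with washout. The number of patients is unknown and may be small or nil. No bias or loss of precision in any endpoint is shown or claimed. The text should be amended because the gap concerns consent and safety and the remedy is cheap.

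**What to change.** Add to exclusion 8, and repeat in the Screening/Baseline text of Section 5: *If a prohibited medication is stopped for study eligibility and not as ordinary care, written informed consent is obtained before the washout starts (for example, at the pre-screening approach); AEs and SAEs are recorded from that consent; and the date of stopping is recorded.*

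Optionally, add a footnoted AE mark at Screening/Baseline in the procedures table for these patients. This would only bring the table into line with Section 7. The consent sentence is the necessary part.

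The cost is amendment wording and one earlier consent contact for each patient affected, a small burden on site and patient. No test, scan or additional scheduled visit is needed for other participants.
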